## **12. APPENDIX A: SUB-STUDY A: SASANLIMAB + ENCORAFENIB + BINIMETINIB**

### **12.1. Schedule of Activities (SoA): Sub-Study A**

The [SoA](#) table provides an overview of the sub-study visits and procedures. Refer to [Section 8](#) of the master protocol and [Section 12.8](#) of this sub-study appendix for detailed information on each procedure and assessment required for compliance with the protocol.

The investigator may schedule unplanned visits in addition to those listed in the [SoA](#) table, in order to conduct evaluations or assessments required to protect the well-being of the participant, or if otherwise clinically indicated.

**Table 5. Schedule of Activities Sub-Study A Phase 1b and Phase 2**

Visit Identifier a Abbreviations used in this table may be found in Appendix 11, Section 10.11	Screening b (≤28 days prior to first dose)	Treatment Period									Follow-Up e			
		Cycle 1 c (Days 1 to 28)			Cycle 2 c (Days 1 to 28)		Cycle 3 & 4 (Days 1 to 28)	Cycle 5 (Days 1 to 28)		Cycle ≥6 (Days 1 to 28)				
		Day 1	Day 8 (Phase 1b Only)	Day 15	Day 1	Day 15	Day 1	Day 1	Day 8 (Phase 1b Only)	Day 1	EOT d	Day 30 e	Day 60, Day 90, Day 180 e	Survival e
Visit Window			±1	±2	±2	±2	±2	±2	±1	±2		±7	±7	±7
Informed consent f	X													
Tumor and medical history g	X													
Substance and tobacco use	X									X				
Physical examination h	X	X	X	X	X		X	X		X	X			
Height	X													
Weight	X	X			X		X	X		X	X			
Vital signs (BP/pulse rate/temp) i	X	X	X	X	X		X	X		X	X	X		
ECOG performance status j	X	X												
Triplicate 12-lead ECG k	X	X												
Single 12-lead ECG k			X	X	X		X	X	X	X	X	X		
Echocardiogram/MUGA l	X						X (C3 only)			C6D1, C9D1, C12D1, and every 6 months thereafter	X			
Ophthalmic examination m	X													
Visual acuity exam m	X	X			X		X	X		X				
Dermatologic exam	X	X					X (C3 only)	X		C7D1 and then every	X	X		

**Table 5. Schedule of Activities Sub-Study A Phase 1b and Phase 2**

Visit Identifier a Abbreviations used in this table may be found in Appendix 11, Section 10.11	Screening b (≤28 days prior to first dose)	Treatment Period										Follow-Up e		
		Cycle 1 c (Days 1 to 28)			Cycle 2 c (Days 1 to 28)		Cycle 3 & 4 (Days 1 to 28)	Cycle 5 (Days 1 to 28)		Cycle ≥6 (Days 1 to 28)				
		Day 1	Day 8 (Phase 1b Only)	Day 15	Day 1	Day 15	Day 1	Day 1	Day 8 (Phase 1b Only)	Day 1	EOT d	Day 30 e	Day 60, Day 90, Day 180 e	Survival e
										8 weeks thereafter				
Laboratory Assessments of Hematology and Blood Chemistry n	X	X	X	X	X	X	X	X	X	X	X	X		
Coagulation n	X	X		X		X	X		X	X	X			
Urinalysis o	X	X								X	X			
Pregnancy test p	X	X		X		X	X		X	X	X	X		
Hepatitis B, C tests q	X													
Endocrinology tests n	X					Every 4 cycles starting at C4D1								
Allocation to study intervention r		X												
Administration of study treatment (sasanlimab) s		X			X		X	X		X				
Administration of study treatment (encorafenib) t		Continuous QD												
Administration of Study treatment (binimetinib) u		Continuous BID												
Dispensing of encorafenib and binimetinib		X			X		X	X		X				
Local site injection tolerability assessment v		X			X		X	X		X				
Tumor assessment w	X	Every 8 wks (±7 days) from C1D1 for the first 18 months, then every 12 wks (±7 days) thereafter according to calendar, regardless of treatment delays and until progressive disease assessed by investigator using RECIST v1.1 or start of new anti-cancer therapy												
Patient Reported Outcomes: EORTC QLQ-C30/LC13 x		X			X		X	X		X	X			

**Table 5. Schedule of Activities Sub-Study A Phase 1b and Phase 2**

Visit Identifier a Abbreviations used in this table may be found in Appendix 11, Section 10.11	Screening b (≤28 days prior to first dose)	Treatment Period										Follow-Up e		
		Cycle 1 c (Days 1 to 28)			Cycle 2 c (Days 1 to 28)		Cycle 3 & 4 (Days 1 to 28)	Cycle 5 (Days 1 to 28)		Cycle ≥6 (Days 1 to 28)				
		Day 1	Day 8 (Phase 1b Only)	Day 15	Day 1	Day 15	Day 1	Day 1	Day 8 (Phase 1b Only)	Day 1	EOT d	Day 30 e	Day 60, Day 90, Day 180 e	Survival e
Nonserious and serious adverse events y	X	→	→	→	→	→	→	→	→	→	→	→	→	→
Prior and Concomitant medication/surgery/radiation & non-drug supportive interventions z	X	X	X	X	X	X	X	X	X	X	X	X		
Survival & subsequent anti-cancer therapy										X	X	X	X	
Contraception check aa	X	X			X		X	X		X	X	X		
Remote visit						X						X	X	
PK, Pharmacodynamic, Pharmacogenomic, and Immunogenicity														
Sasanlimab PK bb		X	X	X	X		X (C3 only)	X	X	X (C7, C10, C13, then every 6 cycles until EOT)				
Encorafenib PK cc		X		X	X			X						
Binimetinib PK cc		X		X	X			X						
Blood biospecimen to confirm eligibility dd	X													
Baseline tumor biopsy ee	X													
Biobanked biospecimen for genetics ff		X												

**Table 5. Schedule of Activities Sub-Study A Phase 1b and Phase 2**

Visit Identifier a Abbreviations used in this table may be found in Appendix 11, Section 10.11	Screening b (≤28 days prior to first dose)	Treatment Period										Follow-Up e			
		Cycle 1 c (Days 1 to 28)			Cycle 2 c (Days 1 to 28)		Cycle 3 & 4 (Days 1 to 28)	Cycle 5 (Days 1 to 28)		Cycle ≥6 (Days 1 to 28)					
		Day 1	Day 8 (Phase 1b Only)	Day 15	Day 1	Day 15	Day 1	Day 1	Day 8 (Phase 1b Only)	Day 1	EOT d	Day 30 e	Day 60, Day 90, Day 180 e	Survival e	
Blood for cell-free (cf) DNA analysis gg		X			X						X				
Blood for specified genetic research hh	X	X		X	X										
Blood for T-Cell Receptor (TCR) analysis kk	X	X		X	X										
Immunogenicity for sasanlimab ll		X			X				X		X				

- Day relative to start of study intervention (Day 1).
- Screening:** To be performed within 28 days prior to first dose. Visit may be conducted over multiple days.
- For Phase 1b, during Cycle 1, the D1, D8, and D15 visits occur in clinic. For Phase 1b, during Cycle 2, only D1 visit occurs in clinic and for D15 only clinical laboratory assessments will be performed. For Phase 2, during Cycle 1, Day 1 visit occurs in clinic, no Day 8 visit occurs, and Day 15 will be on-site full visit. For Phase 2 Cycle 2, Day 1 in clinic and Day 15 labs occur locally.
- End of Treatment (EOT) Visit:** See Section 8.11. Conducted at the visit that the participant is discontinued from study treatment or no longer than 1 week after the decision to discontinue the participant from study drug.
- Follow-up:** See Section 8.2.8. The initial safety follow-up visit will be conducted at the study clinic 30 days after the last dose of study drug. The 60, 90, and 180-day follow-up may be conducted by remote contact (eg. telephone). **Survival Follow-up:** See Section 8.1.3. Only to be performed for participants enrolled in Phase 2. Participants will be contacted every 12 weeks (±7 days) after the last clinic visit until death, lost-to-follow-up, study discontinued by sponsor, end of study, or participant withdrawal of consent of study, whichever comes first.
- Informed Consent:** Must be obtained prior to undergoing any study specific procedures. May be obtained more than 28 days prior to first dose.

**Table 5. Schedule of Activities Sub-Study A Phase 1b and Phase 2**

Visit Identifier a Abbreviations used in this table may be found in Appendix 11, Section 10.11	Screening b (≤28 days prior to first dose)	Treatment Period									Follow-Up e		
		Cycle 1 c (Days 1 to 28)			Cycle 2 c (Days 1 to 28)		Cycle 3 & 4 (Days 1 to 28)	Cycle 5 (Days 1 to 28)		Cycle ≥6 (Days 1 to 28)			
		Day 1	Day 8 (Phase 1b Only)	Day 15	Day 1	Day 15	Day 1	Day 1	Day 8 (Phase 1b Only)	Day 1	EOT d	Day 30 e	Day 60, Day 90, Day 180 e

- g. **Tumor History:** Includes history of disease under study including details of primary diagnosis, treatment history, staging, and molecular profiling data (if available). **Medical History:** Includes history other than the cancer under study. Abnormalities observed during screening are to be considered as medical history.
- h. **Physical examination (PE):** See [Section 8.2.1](#).
- i. **Vital Signs:** See [Section 8.2.2](#). Includes temperature, blood pressure (BP), pulse rate. On Day 1 of each cycle, vital signs are to be measured prior to administration of any study drug (pre-dose).
- j. **Eastern Cooperative Oncology Group (ECOG) Performance Status:** See [Section 8.2.6](#).
- k. **Triplicate/Single 12 Lead electrocardiogram (ECG):** See [Section 8.2.3](#). When triplicate ECG is requested, 3 serial 12-lead ECGs will be conducted within approximately 5-10 minutes total time. Triplicate ECGs on C1D1 will be collected prior to administration of any study drug. For remaining timepoints, single ECG will be collected prior to administration of study drug. When coinciding with blood sample draws for PK, ECG assessment is to be performed prior to blood sample collection, such that the blood sample is collected at the nominal time.
- l. **Echocardiogram or multigated acquisition (MUGA) Scan:** [Section 12.8.2.1](#). The same modality used during screening is to be used for all subsequent timepoints. Assessment will also be performed if a participant experiences an AE which may be related to cardiac dysfunction in the opinion of the investigator.
- m. **Ophthalmic Examination:** See [Section 12.8.2.3](#).
- n. **Hematology, Blood Chemistry, Endocrinology, and Coagulation assays:** See [Appendix 2 \(Section 10.2\)](#) and [Section 12.10.1](#) for Laboratory Tests list. Not necessary to repeat on C1D1 if performed within 7 days prior to C1D1 as part of Screening. Subsequent assessments must be performed within 72 hours prior to the scheduled visit. Hematology and chemistry assessments on Cycle 2 Day 15 may be drawn at a lab local to the participant and do not require on-site visit.
- o. **Urinalysis:** Dipstick is acceptable. No need to repeat on C1D1 if baseline assessment is performed within 72 hours prior to that date. See [Section 10.2](#) and [Section 12.10.1](#) for urinalysis details.
- p. **Pregnancy Test (Serum/Urine):** For female participants of childbearing potential, a serum or urine pregnancy test, with sensitivity of at least 25 mIU/mL, will be performed on 2 occasions prior to starting study therapy, once at screening and once at the C1D1 visit before dosing. Participants with a confirmed positive pregnancy test(s) must not be dosed. Pregnancy tests will also be routinely performed throughout the study as per [SoA](#) and additionally whenever 1 menstrual cycle is missed or when potential pregnancy is otherwise suspected. Additional pregnancy tests may also be performed if requested by IRB/EC or if required by local regulations. At the 60, 90, and 180-day remote follow-up visits, pregnancy tests may be conducted via home kits.

**Table 5. Schedule of Activities Sub-Study A Phase 1b and Phase 2**

Visit Identifier a Abbreviations used in this table may be found in Appendix 11, Section 10.11	Screening b (≤28 days prior to first dose)	Treatment Period									Follow-Up e		
		Cycle 1 c (Days 1 to 28)			Cycle 2 c (Days 1 to 28)		Cycle 3 & 4 (Days 1 to 28)	Cycle 5 (Days 1 to 28)		Cycle ≥6 (Days 1 to 28)			
		Day 1	Day 8 (Phase 1b Only)	Day 15	Day 1	Day 15	Day 1	Day 1	Day 8 (Phase 1b Only)	Day 1	EOT d	Day 30 e	Day 60, Day 90, Day 180 e

- q. **Hepatitis B, C:** In the case of apparent ongoing HBV or HCV infection, reflex serum viral load testing will be performed.
- r. **Allocation:** The participant allocation number will be assigned using an IRT system. Participants can be allocated in IRT no more than 3 days prior to dosing.
- s. **Study Treatment (sasanlimab):** Will be administered once every 28 days as 1 SC injection totaling 300 mg.
- t. **Study Treatment (encorafenib):** Once daily oral administration. See [Section 12.6](#) for details.
- u. **Study Treatment (binimetinib):** Twice daily oral administration. See [Section 12.6](#) for details.
- v. **Local Site Injection Tolerability Assessment for sasanlimab:** See [Section 8.2.7](#).
- w. **Tumor Assessments:** See [Section 8.1.1](#) and [Section 12.8.1.1](#). Tumor response assessments will be determined in accordance with RECIST v1.1.
- x. **Patient Reported Outcome:** Required in Phase 2 only. The questionnaires should be administered prior to any other scheduled assessments or drug administrations. See [Section 12.8.5](#).
- y. **Nonserious and Serious AE Assessments:** See [Section 8.3](#). AEs and SAEs are documented and recorded at each visit using NCI CTCAE version 5.0.
- z. **Concomitant Medications and Non-Drug Supportive Interventions:** Includes supportive care drugs (eg, anti-emetic treatment and prophylaxis), drugs used to treat AEs or chronic diseases, and non-drug supportive interventions (eg, transfusions). Reporting period for concomitant medications for AEs and SAEs are to follow respective AE and SAE reporting period.
- aa. **Contraceptive Check:** See [Section 12.10.2](#). Male participants who are able to father children and female participants who are of childbearing potential will need to affirm that they meet the criteria for correct use of the selected methods of contraception throughout the study and continue for 6 months after the last dose. The investigator or his or her designee will discuss with the participant the need to use the appropriate contraception methods consistently and correctly and document such conversation in the participant’s chart. The investigator or his or her designee will instruct the participant to call immediately if the selected contraception methods are discontinued, or if pregnancy is known or suspected in the participant or participant’s partner.
- bb. **Blood for sasanlimab PK:** One 3-mL sample will be drawn for sasanlimab on each day indicated on the [SOA](#). All samples taken on Day 1 of a cycle will be collected within 6 hours prior to dosing of sasanlimab.
- cc. **Blood for encorafenib and binimetinib PK:** One 5-mL sample will be drawn for both encorafenib and binimetinib PK on each day indicated on the [SOA](#). All samples will be collected within 2 hours prior to dosing of either encorafenib or binimetinib.
- dd. **Biospecimen to confirm eligibility:** See [Section 8.7.1](#). A 20-mL blood sample will be collected to confirm eligibility via ctDNA assay. In Phase 2, if ctDNA assay results cannot be interpreted, reflex testing of tumor tissue will be initiated. This blood sample may also be used for possible future development of a medical device/diagnostic test (See [Section 12.8.4](#)).

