### 8.2.8. 30/60/90/180 Day Follow-Up Visits

The initial safety follow-up visit will be conducted in the clinic 30 days after last dose of study drug. The 60-, 90-, and 180-day follow-up visits will be performed via remote contact (eg, telephone). The investigator may conduct these follow-up visits in clinic if any concerns are noted during the remote contact. Refer to [Section 8.1.1](#) for guidance on tumor assessment during the Follow-up periods. Refer to the respective sub-study [SoA](#).

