### **10.12.2. Telehealth Visits**

In the event that in-clinic study visits cannot be conducted, every effort should be made to follow up on the safety of study participants at scheduled visits per the Schedule of Activities or unscheduled visits. Telehealth visits may be used to continue to assess participant safety and collect data points. Telehealth includes the exchange of healthcare information and services via telecommunication technologies (e.g., audio, video, video-conferencing software) remotely, allowing the participant and the investigator to communicate on aspects of clinical care, including medical advice, reminders, education, and safety monitoring. The following assessments must be performed during a telehealth visit:

- Review and record any AEs and SAEs since the last contact. Refer to [Section 8.3](#).
- Review and record any new concomitant treatments or changes in concomitant treatments since the last contact.
- Review and record contraceptive method and results of pregnancy testing if applicable for the participant. Confirm that the participant is adhering to the contraception method(s) required in the protocol. Refer to [Section 10.12.3.1](#) of this appendix regarding pregnancy tests.
- Assess ECOG performance status.

Study participants must be reminded to promptly notify site staff about any change in their health status.

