#### **12.10.2.1. Male Participant Reproductive Inclusion Criteria**

Male participants are eligible to participate if they agree to the following requirements during the intervention period and for at least 6 months after the last dose of study intervention, which corresponds to the time needed to eliminate reproductive safety risk of the study intervention(s):

- Refrain from donating sperm.

PLUS either:

- Be abstinent from heterosexual intercourse with a female of childbearing potential as their preferred and usual lifestyle (abstinent on a long-term and persistent basis) and agree to remain abstinent.

OR

- Must agree to use a male condom when engaging in any activity that allows for passage of ejaculate to another person.
- In addition to male condom use, a highly effective method of contraception may be considered in WOCBP partners of male participants (refer to the list of highly effective methods below in [Section 12.10.2.4](#)).

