**Table 23. Schedule of Activities Sub-Study B Phase 1b & Phase 2**

Visit Identifier a	Pre-Screening b	Screening b (≤28 days prior to first dose)	Treatment Period									Follow-Up d		
			Cycle 1 (Days 1 to 21)		Cycle 2 (Days 1 to 21)		Cycles 3 & 4 (Days 1 to 21)		Cycle 5 (Days 1 to 21)		Cycles ≥ 6 (Days 1 to 21)			
			Day 1	Day 8	Day 1	Day 8	Day 1	Day 1	Day 8	Day 1	EOT c	Day 30 d	Days 60, 90, & 180 d	Survival d
Administration of study treatment sasanlimab f			X		X			X	X		X			
Administration of study treatment SEA-TGT s			X		X			X	X		X			
Administration of study treatment axitinib t			Continuous BID starting C1D1											
Local site injection tolerability assessment u			X		X			X	X		X			
Tumor assessment v		X	Every 6 wks (±7 days) from C1D1 for the first 12 months, then every 12 wks (±7 days) thereafter according to calendar, regardless of treatment delays and until progressive disease assessed by investigator using RECIST v1.1 or start of new anti-cancer therapy											
Nonserious and serious adverse events w		X	→	→	→	→	→	→	→	→	→	→	→	→
Prior and Concomitant medication/surgery/ radiation & non-drug supportive interventions x		X	X	X	X			X	X	X	X	X		
Survival & subsequent anti-cancer therapy											X	X	X	X
Contraception check y		X	X		X			X	X		X	X	X	
Remote visit						X							X	X
PK for sasanlimab z			X	X	X			X	X	X	X (C7, C10, C13, C16, then every 6 cycles)			

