- v. **Tumor Assessments:** Tumor response assessments will be determined in accordance with RECIST v1.1. See [Section 8.1.1](#).
- w. **Nonserious and Serious AE Assessments:** AEs and SAEs are documented and recorded at each visit using NCI CTCAE version 5.0. See [Section 8.3](#).
- x. **Concomitant Medications and Non-Drug Supportive Interventions:** Includes supportive care drugs (eg, anti-emetic treatment and prophylaxis), drugs used to treat AEs or chronic diseases, and non-drug supportive interventions (eg, transfusions). Reporting period for concomitant medications for AEs and SAEs are to follow respective AE and SAE reporting period. See [Sections 6.5](#) and [13.6.5](#).
- y. **Contraceptive Check:** Male participants who are able to father children and female participants who are of childbearing potential will need to affirm that they meet the criteria for correct use of the selected methods of contraception throughout the study and continue for 6 months after the last dose. The investigator or his or her designee will discuss with the participant the need to use the appropriate contraception methods consistently and correctly and document such conversation in the participant’s chart. The investigator or his or her designee will instruct the participant to call immediately if the selected contraception methods are discontinued, or if pregnancy is known or suspected in the participant or participant’s partner. See [Section 13.10.2](#).
- z. **PK for sasanlimab:** One 3-mL blood sample will be collected for sasanlimab PK on each day indicated in the [SoA](#). All samples taken on Day 1 of a cycle will be collected within 6 hours prior to dosing of sasanlimab. The PK sample may be collected anytime during the visit on sampling days that are not Day 1 of a cycle.

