#### 13.10.2.1. Male Participant Reproductive Inclusion Criteria

Male participants are eligible to participate if they agree to the following requirements during the intervention period and for at least 6 months after the last dose of study intervention, which corresponds to the time needed to eliminate reproductive safety risk of the study intervention(s):

- Refrain from donating sperm.

PLUS either:

- Be abstinent from heterosexual intercourse with a female of childbearing potential as their preferred and usual lifestyle (abstinent on a long-term and persistent basis) and agree to remain abstinent.

OR

- Must agree to use contraception/barrier as detailed below:
  - Agree to use a male condom when engaging in any activity that allows for passage of ejaculate to another person.
  - In addition to male condom use, a highly effective method of contraception may be considered in WOCBP partners of male participants (refer to the list of highly effective methods below in [Section 13.10.2.4](#)).

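### The contraception check stops at Day 30 in both schedules, although contraception is required for 6 months and calls at Days 60, 90 and 180 already take place

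*Protocol*

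**What the plan says.** **Duration of the duty.** Table 5 footnote aa asks men who can father children and women of childbearing potential to affirm the "criteria for correct use of the selected methods of contraception throughout the study and continue for 6 months after the last dose". Table 23 footnote y has them "continue for 6 months after the last dose" as well. The eligibility text repeats the period for men. In Sub-Study A (Section 12.10.2.1), "Male participants are eligible to participate if they agree to the following requirements during the intervention period and for at least 6 months" beyond their final dose. In Sub-Study B (Section 13.10.2.1) the period is "for at least 6 months after the last dose of study intervention". Sections 12.10.2.2 and 13.10.2.2 set the same period for women.

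**When it is checked.** Section 5.3.1 places the reminder, the participant's affirmation and the chart documentation at the time points in the schedule of activities. The row named "Contraception check" in each table therefore decides when a check takes place.

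**Contacts after Day 30.** Section 8.2.8 provides them: "The 60-, 90-, and 180-day follow-up visits will be performed via remote contact (eg, telephone"). Table 5 footnote p and Table 23 footnote o add pregnancy tests at those contacts, with home kits allowed, for women of childbearing potential only.

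**Checks by telephone.** For telehealth visits in a public emergency, Section 10.12.2 lists as a required item: "Review and record contraceptive method and results of pregnancy testing if applicable for the participant". It also asks the site to confirm adherence.

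**The concern.** The protocol gives its own reasons for the 6-month period. Section 12.2.2.1 states that encorafenib or binimetinib can harm the fetus. Sections 12.10.2 and 13.10.2 state that sasanlimab may carry a developmental risk that has not been studied. Yet scheduled reinforcement ends one month into the six.

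For women, the later pregnancy tests can detect a pregnancy but do nothing to prevent one. Fertile men must use condoms or abstain for the whole period, and Section 8.3.5.1 collects partner pregnancies to 6 months, but after Day 30 no scheduled item asks them about either. At Day 30 a participant can promise five more months of contraception. No later scheduled question asks whether it was kept up. What is at stake is avoidable fetal exposure and late capture of partner pregnancies. No endpoint, error rate or sample size is affected.

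**Working it through.** No formula in the plan is at issue. The check is to locate the last mark in the contraception row of each schedule.

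**Table 5 (Sub-Study A).** The row has 14 cells for 14 visit columns. Marks fall in cells 1, 2, 5, 7, 8, 10, 11 and 12. Read against the header, these are Screening, C1D1, C2D1, Cycles 3/4, C5D1, Cycle 6 onward, EOT and Day 30. The Day 60/90/180 and Survival cells are empty.

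**Table 23 (Sub-Study B).** The extracted row has marks in cells 2, 3, 5, 8, 9, 11, 12 and 13. Taken literally, that gives Screening, C1D1, C2D1, C5D1, C5D8, EOT, Day 30 and Day 60/90/180, with no check in Cycles 3/4 or from Cycle 6 onward. The row "Administration of study treatment sasanlimab" on the same page has marks in cells 3, 5, 8, 9 and 11. Sasanlimab is given on Day 1 of every cycle, so cells 8, 9 and 11 can only be Cycles 3/4, C5D1 and Cycle 6 onward. The text has gained one empty cell after Cycle 2. With the same correction, contraception cells 8, 9, 11, 12 and 13 become Cycles 3/4, C5D1, Cycle 6 onward, EOT and Day 30.

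**Cross-check by count.** The number of marks does not depend on how the columns line up.

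| Row | Marks | Visits that account for them |
|---|---|---|
| Contraception check, Table 5 | 8 | Screening, C1D1, C2D1, C3/4, C5D1, C≥6, EOT, Day 30 |
| Contraception check, Table 23 | 8 | the same eight |
| Pregnancy test, Table 5 | 9 | the same eight plus Day 60/90/180 (footnote p) |
| Pregnancy test, Table 23 | 9 | the same eight plus Day 60/90/180 (footnote o) |

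The pregnancy row has exactly one mark more, and the footnotes place that mark at the remote contacts. A contraception mark at Day 60/90/180 would require one of the earlier visits, in practice a treatment visit or EOT, to go unchecked.

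**Size.**
- Remote contacts with a contraception check: 0 of 3 in each sub-study.
- Remote contacts with a pregnancy test: 3 of 3 for women of childbearing potential, 0 of 3 for men.
- Interval without a scheduled check: 180 − 30 = 150 days, and 150/180 = 83% of the required period, taking 6 months as the 180 days of the last contact.

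This is calendar time, not a pregnancy risk. The protocol gives no number of fertile participants from which a risk could be worked out.

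**The case against.** **The tables are broken.** Other rows on the same pages are displaced, and not all in the same direction. In Table 5 the survival and remote-visit rows sit one column too far left; read literally they would make Day 30 a remote visit, which Section 8.2.8 contradicts. In Table 23 those two rows look correctly placed in the follow-up columns. The concomitant-medication row there, if shifted like the dosing row, would end at EOT, against the 30 days in Section 6.5. So a row that fills 14 cells is not proof of position, and the dosing row has no marks in follow-up. This stands as a caution and is why the original pages should be checked, for Table 23 above all. It does not overturn the reading, because the count of eight against nine and the pattern of marks within the contraception row both point to Day 30.

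**Nothing is contradicted.** The duty binds for 6 months, no text demands a monthly check, and the affirmation at EOT and Day 30 looks forward. Participants of both sexes are told to call if contraception stops or pregnancy is suspected, including in a partner. Exposure during pregnancy is reportable within 24 hours. Adverse event collection runs to at least 90 days and could bring a partner pregnancy to light. The amendment history shows that the Day 180 contact and home tests were added on advice about contraception and pregnancy testing, so follow-up content was considered. All of this holds, and it limits the point to a minor one. For men, however, these safeguards depend on the participant raising the matter: adverse event questioning is deliberately nonleading, and no scheduled question covers contraception. The same advice led to testing at the remote contacts, but the check was not carried over to them.

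**Conclusion.** The concern holds, as a minor gap in scheduled reinforcement. After Day 30 neither sub-study schedules a contraception check for anyone, and neither schedules any contraception or pregnancy item for fertile men, for 150 of the 180 days. Women of childbearing potential are still tested at all three remote contacts.

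This rests on two assumptions: that the eight marks in each contraception row are the visits listed above, to be confirmed on the original tables, and that 6 months is taken as Day 180. The effect is on participant safety and site procedure; no analysis changes.

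**What to change.** Mark the contraception check in the Day 60/90/180 column of Tables 5 and 23. Use the Section 10.12.2 content for these calls: review the method and confirm adherence. For male participants, add a direct question on known or suspected partner pregnancy, in line with the call-the-site instruction in footnotes aa and y.

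The cost is one mark in each table and a short question with a chart note at three calls that already take place. There is no new visit or sample, and no new CRF field, since Section 5.3.1 keeps contraception details out of the CRF. The change can go into the next amendment.
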